10.0 Data and Specimen Banking: N/A

11.0 Data Analysis and Management

The primary outcome measure will be the percentage of intraoperative time above a body temperature of 36° C. Melton GB at el. reported the absolute percentage of time above

Page 7 of 19 Revised Template: December 12, 2017

A Prospective Randomized Evaluation of Two Perioperative Active Warming Techniques for Maintenance of Normothermia in Colorectal Surgeries the threshold of 36 °C was 57% in patients receiving standard forced air warming intraoperatively. (10)

The number of subjects (N=146) was determined for two groups of 73 in each group to achieve 83% power to detect a difference of 10% between the active warming underbody mattress and forced air warming device, assuming that the standard forced air warming method would achieve a value of 57% and that non-inferiority would be set as a marginal difference of -10%. This sample would provide a significance level of 0.042 using a onesided Z test. Seven patients will be added to each group for protocol violations and data lost in follow up making 160 the total number of subjects that will be recruited.

Interim analysis is preplanned with two looks at n=74 and n=146. Significance and futility boundaries for look 1 and 2 are set at:

Boundaries for Scenario 1

	Significanc	e Boundary	Futility Boundary	
	Z-Value	P-Value	Z-Value	P-Value
Look	Scale	Scale	Scale	Scale
1	2.72119	0.00325	0.16669	0.43381
2	1.54065	0.06170	1.54065	0.06170

The data will be stored in a departmental password-protected computer with a 5-minute logout. This computer is accessed behind locked departmental doors. Participants will each be assigned an ID number, which will be used as the sole identifier on any documents. Subject data will be compiled onto a single password protected file, where they will only be identified by their ID number. An enrollment log will be the only file where subject names are correlated with ID numbers. This will be kept in a separate, secure, password-protected file in the Department of Anesthesiology. Confidentiality is secured after transferring the data from paper questionnaires to a password protected departmental computer which is uploaded to the departmental server, which is also password protected with limited access to study team only. Data (both electronic and paper) will be destroyed 3 years after data analysis using current departmental standards and vendors. The completed data set is controlled by the PI and only select study team members will have access to the data set. The data set will not be transported. The departmental computer is located at the Department of Anesthesiology, [name].

11.1 Describe how data will be handled study-wide:

- What information will be included in that data?

 The information on the data sheet, patient code identifier list and a copy of the consent.
- Where and how data will be stored?
 Department of Anesthesiology, Arkes Pavilion 10th Floor.
- How long the data will be stored?

Page 8 of 19 Revised Template: December 12, 2017

The data both electronic and paper will be destroyed 3 years after manuscript completion using departmental approved methods of destruction.

- Who (role on the study) will have access to the data?
 Authorized study personnel will have access to the data.
- Who (role on the study) is responsible for receipt or transmission of the data? Principal Investigator
- How data will be transported?
 All paper data sheets will be kept in binders and stored in a locked cabinet in the department of Anesthesiology. Paper data will then be logged into in a single computer in the department of Anesthesiology by authorized research personnel.

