PROTOCOL TITLE:

A Prospective Randomized Evaluation of Two Perioperative Active Warming Techniques in Maintenance of Normothermia in Colorectal Surgeries

PRINCIPAL INVESTIGATOR:

[name]. Department of Anesthesiology [contact] [contact]

CO-INVESTIGATOR

[name]. Department of Anesthesiology [contact] l- [contact]

VERSION NUMBER: 1.1

VERSION DATE: 12.12.2017

Industry Clinical Trial: VitaHeat Medical, Inc.

Table of Contents

1.0	Objectives	3
2.0	Background	3
3.0	Inclusion and Exclusion Criteria	3
4.0	Study-Wide Number of Subjects	3
5.0	Study-Wide Recruitment Methods	3
6.0	Multi-Site Research	4
7.0 St	tudy Timelines	4
8.0 S	tudy Endpoints	4
9.0	Procedures Involved	4
10.0	Data and Specimen Banking	5
11.0	Data and Specimen Management	5
12.0	Provisions to Monitor the Data to Ensure the Safety of Subjects	6
13.0	Withdrawal of Subjects*	6
14.0	Risks to Subjects*	6
15.0	Potential Benefits to Subjects	7
16.0	Vulnerable Populations.	7

Page 1 of 19

17.0	Community-Based Participatory Research	7
18.0	Sharing of Results with Subjects	8
19.0	Setting	8
20.0	Resources Available	8
21.0	Prior Approvals	9
22.0	Recruitment Methods	9
23.0	Local Number of Subjects	9
24.0	Confidentiality	10
25.0	Provisions to Protect the Privacy Interests of Subjects	
26.0	Compensation for Research-Related Injury	10
27.0	Economic Burden to Subjects	10
28.0	Consent Process	10
29.0	Process to Document Consent in Writing.	13
30.0	Budget	14
31.0	Drugs or Devices.	14
32.0	Financial Disclosure	14

1.0 **Objectives**

We propose a study in which we compare two intraoperative active warming devices for maintenance of normothermia in patients undergoing colorectal surgery. A novel underbody resistive warming mattress (VitaHeat Medical) will be compared to the forced air warming blanket (3M Bair Hugger) that is currently used in our institution.

Our hypothesis is that the underbody resistive warming mattress will be equally effective as forced air warming in maintaining normothermia in colorectal surgery.

2.0 **Background**

In humans, maintenance of core temperature is tightly regulated by the thermoregulatory center in the hypothalamus. However, skin temperature varies in differing ambient temperatures due to continuous heat transfer. Heat transfer from the body to the environment occurs by convection, conduction, radiation and evaporation. (1)

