3.0 Inclusion and Exclusion Criteria

- 3.1 All patients' ≥18 years of age who are scheduled to undergo laparoscopic or open colorectal surgical procedures under general anesthesia are eligible to participate.
- 3.2 **Inclusion:** Eligible subjects will include patients 18 years of age undergoing laparoscopic or open colorectal surgical procedures under general anesthesia.

Exclusion: Patients less than 18 years of age, emergent surgery, thyroid problems, preoperative fever and pregnant patients.

- Adults unable to consent: *Exclude*
- Individuals who are not yet adults (infants, children, teenagers): *Exclude*
- Pregnant women: *Exclude*
- Prisoners: Exclude
- 4.0 Study-Wide Number of Subjects: N/A
- 5.0 Study-Wide Recruitment Methods: N/A
- 6.0 Multi-Site Research: N/A
- 7.0 **Study Timelines**
 - 7.1 Describe:
 - The duration of an individual subject's participation in the study: 30 days
 - The duration anticipated to enroll all study subjects.12/31/2018

 ☐ The estimated date for the investigators to complete this study (complete primary analyses).03/01/2019.

8.0 **Study Endpoints**

- 8.1 The primary outcome measure will be the percentage of intraoperative time above a body temperature of 36°C.
- 8.2 The secondary outcomes will be the amount of blood or blood product transfusion, surgical site infections as defined by National surgical quality improvement project (NSQIP) and other infections such as urinary tract infections, pneumonias, cardiac events such as cardiac arrest and myocardial infarction, thromboembolic complications (DVT/PE). Length of hospital stay will be recorded as will length of stay, time to return of bowel function (time to first flatus) will be recorded. At 30 days following

Page 5 of 19 Revised Template: December 12, 2017

the surgery readmissions to the hospital, the reason for the admission and the length of stay during this additional hospitalization will be recorded.

9.0 **Procedures Involved**

9.1 Study design: A prospective randomized controlled trial.

Stratified randomization will be performed using a computerized randomization table where the strata will be type of surgery (open vs closed) and the treatment will be forced air blanket or underbody mattress warming device. This will allow equal groups of both warming devices in both types of surgery.

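### The stated one-sided level of 0.042 conflicts with the printed two-look boundaries, and the 83% power is not established by the inputs given.

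*Combined protocol and SAP*

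**What the plan says.** Section 1.0 hypothesises that the "underbody resistive warming mattress will be equally effective as forced air warming in maintaining normothermia". The primary endpoint is in sections 8.1 and 11.0: "The primary outcome measure will be the percentage of intraoperative time above a body temperature of" 36°C. Section 9.0 records core temperature every minute, so each patient contributes one value between 0 and 100.

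Section 11.0 sizes the trial as "two groups of 73 in each group to achieve 83% power to detect a difference of 10% between the active warming underbody mattress" (comparator: forced air), "assuming that the standard forced air warming method would achieve a value of 57" percent, and adds that "non-inferiority would be set as a marginal difference of -10" percent. On the error rate it says: "This sample would provide a significance level of 0.042 using a onesided Z test". It then states: "Interim analysis is preplanned with two looks at n=74 and n=146. Significance and futility boundaries for look 1 and 2 are set at" the values in the boundary table. At look 1 these are Z=2.72119 for significance and 0.16669 for futility. At look 2 both are Z=1.54065, with a printed p-value of 0.06170.

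The documents give no SD, no variance model, no assumed true value for the mattress and no direction for the 10% difference. They do not describe the Z statistic beyond one-sided, and do not say whether the futility bound is binding.

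**The concern.** Two things do not fit. First, the final threshold alone has a one-sided p-value of 0.0617, above the 0.042 that the section calls its significance level. A final Z between 1.54 and about 1.72 would show non-inferiority under the table but not under a rule that holds 0.042. Nothing in the plan says which rule governs.

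Second, 83% is the figure that justifies N=146, yet it cannot be traced. A per-patient percentage needs an SD before power can be computed, and none is given. The wording also leaves open whether the 10% is an assumed true advantage or the margin stated again. A reader therefore cannot tell what chance the trial has of showing non-inferiority if the two devices are equal, which is the hypothesis. If the trial failed to show it, the plan could not help decide whether the device or the sample size was the reason.

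**Working it through.** **Inputs from section 11.0.** 73 per group; looks at 74 and 146 in total (37, then 73 per group); control 57%; margin −10 points; one-sided 0.042, z=1.7279; boundaries as printed. The 14 extra patients recruited for losses are left out, as in the plan's own calculation.

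**1. The boundary table on its own terms.** P(Z>2.72119)=0.00325, P(Z>0.16669)=0.43381 and P(Z>1.54065)=0.06170. All match the printed p-values, so the table is internally sound.

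**2. Overall error of the boundaries.** Under the null (true difference −10) the two Z values are bivariate normal with correlation √(37/73)=0.712. This is a large-sample calculation without continuity correction.
- Binding futility: 0.00325 at look 1 + 0.05614 at look 2 = 0.0594.
- Non-binding futility: 0.00325 + 0.05910 = 0.0624.

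The stated figure is 0.042.

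**3. Attempts to recover 83%.** Without an SD, the only variance that the printed inputs supply is the binomial p(1−p).
- *Two proportions, equal at 57%, margin −10.* SE=√(2×0.57×0.43/73)=0.0819. Power at 0.042 is Φ(0.10/0.0819−1.7279)=0.306. With the printed boundaries (binding) it is 0.363.
- *Two proportions, mattress 67% vs 57%, margin −10.* SE=√((0.57×0.43+0.67×0.33)/73)=0.0799. Power at 0.042 is Φ(0.20/0.0799−1.7279)=0.781. With the printed boundaries it is 0.819 (binding) or 0.833 (non-binding).
- *67% vs 57% tested against zero difference.* 0.317 at 0.042; 0.386 in a fixed test at Z=1.54065.
- *Continuity-corrected pooled Z, printed boundaries, binding, 400,000 simulated trials.* Error 0.0427 (47% vs 57%); power 0.773 (67% vs 57%).

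One reading comes near 83% but at an error near 0.06. Another comes near 0.042 but with power near 77%. None gives both.

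**4. Comparison of means at zero true difference.** SE=SD×√(2/73). Fixed-test power is Φ(10/SE−1.7279). The SD that gives 83% is 10/[(1.7279+0.9542)×√(2/73)]=22.5 points. All SDs in the table are assumptions.

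| SD (points) | Fixed test, 0.042 | Printed boundaries, binding | Final Z raised to 1.722, binding |
|---|---|---|---|
| 20 | 90% | 92% | 90% |
| 22.5 | 83% | 86% | 82% |
| 30 | 61% | 67% | 61% |
| 40 | 41% | 47% | 41% |

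**5. Final boundary that would hold 0.042.** With the look-1 bounds kept and the bivariate normal of step 2, solving for an overall error of 0.042 gives a final Z of 1.722 (binding) or 1.738 (non-binding).

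**The case against.** The best defence is that the 10% difference is simply the −10 margin said twice. The true difference is then zero, section 11.0 agrees with section 1.0, and a means test at 0.042 with an SD near 22.5 points gives 83%. That is coherent, and it means that no wrong power calculation has been demonstrated. But the SD is solved backwards from the answer. An SD near 45 with a true 10-point advantage would give 83% equally well (the distance from the margin doubles to 20 points, and so does the SD). Nor does this reading explain the boundary table.

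A second defence is that 0.042 may be the attained size of a particular statistic. A continuity-corrected pooled two-proportion Z comes close, at about 0.043. This stands to the extent that 0.059 and 0.062 apply to an uncorrected Z and not to every possible test. It does not rescue the paragraph, because power under that statistic is about 77%, and because it treats a percentage of time as a yes/no outcome.

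Two stronger readings are tempting. A reader might infer that the sponsor planned on the mattress being 10 points better. That rests on a binomial model that the documents never state, and it yields 78.1% at the stated 0.042. A reader might also infer from the 30.6% binomial figure at equality that the trial is badly underpowered. The endpoint is a per-patient percentage whose SD is not given, and at an SD of 20 the power would be 90%.

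**Conclusion.** The point holds as a conflict within section 11.0 together with an unsupported power figure. The printed boundaries have an overall one-sided error of about 0.059 (binding) or 0.062 (non-binding) against the stated 0.042, assuming a large-sample normal Z without continuity correction. No reading tried returns 83% and 0.042 together from the printed inputs alone. Under the equality hypothesis, 83% at 0.042 needs an SD of about 22.5 points that the documents do not give.

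The 83% is therefore not established. The documents do not show that the trial is underpowered, or that a mattress advantage was assumed. The adequacy of N=146 can be neither confirmed nor rejected as written. The conflict over the error rate needs no assumed SD; the power figures do.

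**What to change.** (a) Adopt one rejection rule for the per-patient percentage. Name the test statistic and say whether futility is binding. For an uncorrected Z there are two consistent options:
- keep the printed boundaries and restate the overall one-sided error as about 0.06 (0.059 binding, 0.062 non-binding); or
- keep 0.042 and the look-1 bounds, and raise the final boundary to about Z=1.722 (binding) or 1.738 (non-binding).

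If another statistic is meant, recompute the boundaries for it.

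(b) Under that rule, restate the 83% as power at zero true difference with margin −10, for a named and sourced SD with a range on both sides of it. Keep the assumed true difference separate from the margin in the wording.

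No change in N is proposed here; the recomputed power will show what N=146 can deliver. The cost is one recalculation and revised wording, with a stated error or power that may look less favourable. With binding futility, raising the final boundary lowers power at equality from 92% to 90% at an assumed SD of 20, and from 67% to 61% at an assumed SD of 30. Keeping the boundaries raises the stated error from 0.042 to about 0.06.

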23.0 Local Number of Subjects

The number of subjects to be accrued is 160. There are two groups of 80 subjects.

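### The printed two-look boundaries carry an overall one-sided type I error of about 0.06 under normal theory, not the stated 0.042

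*Combined protocol and SAP*

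**What the plan says.** Section 11.0 (Data Analysis and Management) is the only statistical specification in the document. It sizes the trial as follows: "The number of subjects (N=146) was determined for two groups of 73 in each group to achieve 83% power", the target being "to detect a difference of 10% between the active warming underbody mattress and forced air warming device", with forced air taken as 57% and a non-inferiority margin of -10%. The error rate is given in one sentence: "This sample would provide a significance level of 0.042 using a onesided Z test".

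The section then says: "Interim analysis is preplanned with two looks at n=74 and n=146". The boundary table reads:

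| Look | Significance Z (p) | Futility Z (p) |
|---|---|---|
| 1 (n=74) | 2.72119 (0.00325) | 0.16669 (0.43381) |
| 2 (n=146) | 1.54065 (0.06170) | 1.54065 (0.06170) |

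The plan does not say how 0.042 was obtained, whether the first-look futility bound is binding, or which form of Z test is meant. Section 8.1 defines the primary outcome as the "percentage of intraoperative time above a body temperature" of 36°C, a continuous percentage for each patient. No standard deviation is given.

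**The concern.** The final-look threshold has a nominal p-value of 0.0617, already larger than the overall level claimed for the whole design. If futility is non-binding, every trial that ends with Z above 1.54065 counts as a success, so the overall type I error cannot be below 0.0617, whatever the first look adds. A single one-sided test at 0.042 with no interim look would need Z of at least 1.728.

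The error at stake is declaring the mattress non-inferior when it is truly 10 points worse, so the mismatch affects the primary conclusion. It also leaves a band of results open to dispute: a final Z between 1.541 and about 1.72 to 1.74 passes by the table but fails a design controlled at 0.042.

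**Working it through.** **Inputs, all from section 11.0.** First look: a = 2.72119 for significance, b = 0.16669 for futility. Second look: c = 1.54065. Information fraction t = 74/146 = 0.507. Stated overall one-sided level: 0.042.

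**Step 1: is the table consistent with itself?** 1 - Φ(2.72119) = 0.00325; 1 - Φ(0.16669) = 0.43381; 1 - Φ(1.54065) = 0.06170. All three printed p-values reproduce, so a misread digit is unlikely.

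**Step 2: overall type I error.** At the non-inferiority null (true difference -10 points), Z1 and Z2 are standard bivariate normal with correlation √(74/146) = 0.712. Then

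α = P(Z1 > a) + P(L < Z1 ≤ a, Z2 > c),

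with L = b if futility is binding and L = -∞ if it is not.

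- Binding: 0.00325 + 0.05614 = 0.0594
- Non-binding: 0.00325 + 0.05910 = 0.0624

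Simulation of 4 million trials gives 0.0594 and 0.0624. Relative to the stated level, 0.05939/0.042 = 1.41 and 0.06235/0.042 = 1.48. No variance assumption enters this step.

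**Step 3: does look timing explain it?** With the first look anywhere from 30% to 75% of the information, the total is 0.054 to 0.062 (binding) or 0.062 to 0.063 (non-binding). It never reaches 0.042.

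**Step 4: what final boundary would give 0.042?** Holding the first look as printed and solving for c:

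- Binding: Z = 1.722 (p = 0.0425)
- Non-binding: Z = 1.738 (p = 0.0411)

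**Step 5: which figure does the sample size match?** This step needs two assumptions that the plan does not state: binomial variance, and a true 67% against 57% (mattress 10 points better) tested against the -10 margin. The standardised effect at 73 per arm is

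θ = (0.10 + 0.10)/√[(0.57×0.43 + 0.67×0.33)/73] = 2.503.

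| Rule | Power |
|---|---|
| Printed table, futility obeyed | 81.9% |
| Printed table, futility ignored | 83.3% |
| Single test at Z = 1.54065 | Φ(2.503 - 1.541) = 83.2% |
| Single test at 0.042 | Φ(2.503 - 1.728) = 78.1% |

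On this reading the stated 83% with 73 per arm goes with the 1.54065 boundary. A single test at 0.042 would need 84 per arm for 83%.

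**Step 6: could a discrete test be the source of 0.042?** Exact two-stage binomial calculations (37 then 73 per arm, null 47% against 57%, printed boundaries) give:

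| Z statistic | α binding / non-binding | Power at 67% vs 57%, binding / non-binding |
|---|---|---|
| Pooled, uncorrected | 0.0595 / 0.0636 | 82.5% / 84.0% |
| Unpooled, uncorrected | 0.0636 / 0.0681 | 82.7% / 84.1% |
| Pooled, continuity-corrected | 0.0427 / 0.0469 | 77.4% / 79.5% |
| Unpooled, continuity-corrected | 0.0456 / 0.0504 | 77.4% / 79.6% |

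No variant gives both 0.042 and 83%.

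**The case against.** The strongest reply is that 0.042 may be an achieved level from software using a discrete two-proportion test. The inputs (57%, -10%, no standard deviation) look like such a calculation, and the pooled, continuity-corrected version with binding futility gives 0.0427. On that reading the excess is about 2%. With an uncorrected unpooled test it is as much as 62% (0.0681/0.042 = 1.62). The figure of 59 to 62 per 1,000 is therefore a normal-theory result and should be labelled as one.

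That caution stands, but it does not rescue the plan. The corrected test is not named, its power is about 77% to 80% rather than 83%, and a continuity correction has no natural place with a continuous per-patient percentage. Normal theory is the ordinary reading of a Z test on such an outcome.

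Two further points have merit. The source of 0.042 is unknown, so what can be said is that the level and the table do not agree as written, not which was intended. The power figures also rest on an assumed variance and on an inferred direction for the 10-point difference. Neither point touches the type I error in Step 2.

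Finally, the decision rule itself is explicit and can be carried out, so the defect is a mis-stated operating characteristic. It is still the error rate of the primary test, and it should be settled before data are examined.

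**Conclusion.** The concern holds. Under normal theory, with looks at 74 and 146, the printed boundaries give an overall one-sided type I error of 0.0594 (futility binding) or 0.0624 (non-binding), against 0.042 stated. This rests only on the printed boundaries, the look timing and a normally distributed statistic. It does not depend on the outcome's variance, and neither binding futility (worth about 0.003) nor a different look time closes the gap. A continuity-corrected binomial test could narrow it, but only by giving up the stated power. The level and the boundary table must be reconciled before the primary analysis.

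**What to change.** First, name the test statistic for the primary outcome and state whether the first-look futility bound is binding. Then choose one of the following.

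1. **Keep the table and correct the level.** Replace 0.042 with 0.062, or 0.059 if futility is declared binding. This changes one number and one sentence; the cost is a less favourable stated level. If an uncorrected binomial Z test is named instead, state its own level (0.0595 to 0.0681 in Step 6).
2. **Keep 0.042 and the first look, and reset the final boundary.** Use Z = 1.738 (p = 0.0411) if non-binding or Z = 1.722 (p = 0.0425) if binding, and restate power. Under the Step 5 assumptions, power falls to 77.4% (1.722, futility obeyed), or to 77.9% or 76.9% (1.738, futility ignored or obeyed), about 5 points below the same rule with the printed table. Regaining 83% would need about 85 to 87 evaluable patients per arm with looks scaled. That exceeds the 73 planned and the recruitment in section 23.0: "There are two groups of 80 subjects".

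If 0.042 came from a continuity-corrected test, name that test and restate its level and power (about 77% to 80%).

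Under any option, the restated power should be labelled as resting on an assumed variance, because the plan gives no standard deviation for the per-patient percentage.

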Pre-Op Temp (Oral)	Surgery Type (Circle):
Temp upon arrival to ASU: Time:	Open
Temp at transfer from ASU:Time:	Laparoscopic
Epidural :	Heparin Pre-Op:
Yes / No (Circle Answer)	Yes / No (Circle Answer)
ANESTHESIA PROVIDER: PLEAS	SE COMPLETE BELOW
PATIENT Intra-Op Temp	Patient Position (Circle):
(Core and Skin)	Supine
Ensure that EMR is recording patient	Lithotomy
temperatures at intervals of 1 minute	·
Operating Room Temp	Arm position (Circle):
OR Room temp (upon patient arrival):	On arm boards
OR Room temp (at time of incision):	Tucked
OR Room temp (at time of extubation):	
Warming Device Used (Circle):	Presence of posterior skin
Bair Hugger	surface injury: (for burn injury)
VitaHEAT	
Fluid warmer	Yes No
	If Yes describe:
Anesthesiologist (Print Name):	

Page 14 of 19 Revised Template: December 12, 2017

PACU DATA SHEET

Post-Op Temp (Oral)		Warming Device Used (Circle):
Temp at admission:	Time:	Bair Hugger
Temp at discharge:	Time:	Fluid warmer

Abdominal Surgery Normothermia Patient De-identifier Code List

			illa i atient be-identifier e	
Case	Name	Date of Surgery	Medical Record Number	Telephone #
1				
2				
3				
4				
5				
6				
7				
8				
9				
10				
11				
12				
13				
14				
15				
16				
17				
18				

Page 15 of 19 Revised Template: December 12, 2017

19 20 21 22 23 24 25 26 27	
21 22 23 24 25 26 27	
22 23 24 25 26 27	
23 24 25 26 27	
24 25 26 27	
25 26 27	
26 27	
27	
28	
29	
30	
31	
32	
33	
34	
35	
36	
37	
38	
39	
40	
41	

Page 16 of 19

Revised Template: December 12, 2017

42 43 44 44 45 46 47 48 49 50 51 52 53 54 55 56 57 58 59 60 61 62 63 64 65 65	100111119	 1 (011110 011011	ina in Colorectal Burgeries	
44 45 46 47 48 49 50 51 52 53 54 55 56 57 58 59 60 61 62 63 64	42			
45 46 47 48 49 50 51 52 53 54 55 56 57 58 59 60 61 62 63 64	43			
46 47 48 49 50 51 52 53 54 55 56 57 58 59 60 61 62 63 64	44			
47 48 49 50 51 52 53 54 55 56 57 58 59 60 61 62 63 64	45			
48 49 50 51 52 53 54 55 56 57 58 59 60 61 62 63 64	46			
49 50 51 52 53 54 55 56 57 58 59 60 61 62 63 64	47			
50 51 52 53 54 55 56 57 58 59 60 61 62 63 64	48			
51 52 53 54 55 56 57 58 59 60 61 62 63 64	49			
52 53 54 55 56 57 58 59 60 61 62 63 64	50			
53 54 55 56 57 58 59 60 61 62 63 64	51			
54 55 56 57 58 59 60 61 62 63 64	52			
55 56 57 58 59 60 61 62 63 64	53			
56 57 58 59 60 61 62 63 64	54			
57 58 59 60 61 62 63 64	55			
58 59 60 61 62 63 64	56			
59 60 61 62 63 64	57			
60 61 62 63 64	58			
61 62 63 64	59			
62 63 64	60			
63 64	61			
64	62			

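### No adjustment is stated for the stratification factor or for pre-operative temperature, both already collected; the unadjusted test is valid but may cost precision against the -10 point margin.

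*Combined protocol and SAP*

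**What the plan says.** Section 11.0 gives the design inputs: "two groups of 73 in each group to achieve 83% power to detect a difference of 10" percent, on the assumption that "the standard forced air warming method would achieve a value of 57" percent, while "non-inferiority would be set as a marginal difference of -10" percent. The test is named in the same paragraph, as a "significance level of 0.042 using a onesided Z test". No other test or model for the primary endpoint appears. The conflict-of-interest plan (33.0) adds only that the department statistician will do the analysis.

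Section 9.1 stratifies the randomisation: "the strata will be type of surgery (open vs closed"). Nothing says that the analysis will use the strata.

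The data collection form has a field headed "Pre-Op Temp (Oral"), with timed entries on arrival at the pre-operative unit and for "Temp at transfer from ASU". It also has an untimed yes/no for epidural, and Appendix B asks about epidural again. Under section 9.1 the mattress warms the patient only on the operating table, and forced air starts only after draping. The pre-operative temperatures therefore precede any effect of either device.

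**The concern.** Non-inferiority here depends on how far the lower confidence limit for the arm difference lies from -10 points. Two baseline variables could narrow that limit at no cost, and the plan uses neither.

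- **Surgery type.** Stratifying removes chance imbalance in surgery type between the arms. If surgery type predicts the endpoint, an unadjusted standard error still counts that removed variation. It is then too large, and the test runs below its nominal level.
- **Starting temperature.** The endpoint is time above a fixed threshold, and section 2.0 says that induction moves core heat to the periphery. A patient who starts closer to 36°C plausibly has less room to fall. If so, part of the between-patient variation can be explained before warming begins.

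At stake is power, and with it the chance that an adequate device misses the margin. The same loss would affect the interim look at n=74.

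**Working it through.** **Inputs from section 11.0.** 73 per group, one-sided 0.042, 83% power, control value 57%, margin -10 points. No SD and no R-squared are given, so R-squared is assumed below, over a range.

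**Step 1: the plan's own figure.** Treat 57% as a proportion, with unpooled variance.

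- True difference 0: SE = sqrt(2 × 0.57 × 0.43 / 73) = 0.0819. Power = Φ(0.10/0.0819 − 1.728) = 30.6%.
- True difference +10 points (57% versus 67%): SE = sqrt((0.57 × 0.43 + 0.67 × 0.33)/73) = 0.0799. Power = Φ(0.20/0.0799 − 1.728) = 78.1%.
- The same +10 case with the printed final boundary Z = 1.54065 in place of 1.728: 83.2%. That boundary corresponds to p = 0.0617, not 0.042.

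None of these gives 83% power together with 0.042. Treating the endpoint as continuous with true difference 0, the stated figures require SE = 10/(1.728 + 0.954) = 10/2.682 = 3.73 points. That means SD = 3.73/sqrt(2/73) = 22.5 points, a value the documents do not state. I use this reading only as a starting point for measuring the gain.

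**Step 2: effect of adjustment.** Covariates with joint R-squared R² multiply the standard error by sqrt(1 − R²). Starting from 83%, power = Φ(2.682/sqrt(1 − R²) − 1.728), with no interim look. The same 83% needs 73 × (1 − R²) per group, rounded up.

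| Assumed R² | SE multiplier | Power | n per group for 83% |
|---|---|---|---|
| 0 | 1.000 | 83.0% | 73 |
| 0.05 | 0.975 | 84.7% | 70 |
| 0.10 | 0.949 | 86.4% | 66 |
| 0.20 | 0.894 | 89.8% | 59 |
| 0.30 | 0.837 | 93.0% | 52 |

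The distance from the estimate to the one-sided confidence limit is 1.728 × 3.73 = 6.4 points unadjusted. It is 6.3 points at R² = 0.05 and 5.4 points at R² = 0.30.

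**Step 3: sensitivity to the SD.** Power = Φ(10/(SD × sqrt(1 − R²) × sqrt(2/73)) − 1.728), with both SDs assumed.

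- SD 25: 75.4% at R² = 0; 77.4% at 0.05; 79.4% at 0.10; 83.5% at 0.20; 87.7% at 0.30.
- SD 30: 61.3% at R² = 0; 63.2% at 0.05; 65.4% at 0.10; 70.0% at 0.20; 75.1% at 0.30.

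**Step 4: ignoring the stratification factor.** Suppose the strata alone explain a share R² of the variance and the test ignores them. The actual one-sided error is then about 1 − Φ(1.728/sqrt(1 − R²)). At an assumed R² of 0.10 this is 1 − Φ(1.821) = 0.034, against the nominal 0.042.

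**The case against.** The strongest reply has four parts.

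**The Z test is a sample-size input.** It appears once, in the power paragraph, so a reader might infer that the plan commits to an unadjusted primary analysis. The documents do not go that far: they specify no primary model at all. This stands, and it is why the point is worded as adjustment not being stated. A model still has to be written, and its covariates should be fixed before data are seen.

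**An unadjusted comparison is valid.** A reader might infer bias, or an uncorrected flaw from chance imbalance in starting temperature. Neither follows, because randomisation protects the comparison and its standard error already allows for such imbalance. This stands; the loss is efficiency only.

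**Prognostic value is not documented.** Section 2.0 names duration of surgery, extent of exploration and positioning as contributors to hypothermia. It names neither pre-operative temperature nor epidural use. Excluding preoperative fever also narrows the temperature range. This stands in part: the argument for temperature is mechanistic, and the gain could be close to nil. Surgery type has the better documentary basis, because the trial stratifies on it and extent of exploration is named.

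**Epidural timing is unknown.** A reader might take epidural use as another baseline variable ready for the model. The form's yes/no sits beside a pre-operative item but has no time of placement or activation, and Appendix B asks about it directly after postoperative opioid use. The documents do not establish that it is fixed before randomisation. This stands, so epidural is conditional.

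**Conclusion.** The point holds as a missed gain in precision, not as an error in the plan. On an assumed joint R-squared of 0.05 to 0.30, the standard error falls by 2.5% to 16%. Power rises from the stated 83% to about 85% to 93%, if that 83% at 73 per group and one-sided 0.042 is accepted as the start. At R-squared of 0.05 the gain is under two percentage points; at zero it is nothing.

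A reader might infer that adjustment rescues the sample size. It does not. Under the two-proportion variance with true equality, power moves only from 30.6% to 32.9% (R-squared 0.10) or 39.4% (0.30). The mismatch among the stated power, the 0.042 level and the printed boundaries is a separate problem that needs its own correction.

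**What to change.** State the primary analysis in section 11.0 as a linear model of each patient's percentage of time above 36°C on:

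- arm;
- surgery-type stratum as randomised;
- oral temperature at transfer from the pre-operative area.

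Add epidural (yes/no) only if its status is confirmed as fixed before randomisation. Do not adjust for duration of surgery, which arises after randomisation. State how a missing pre-operative temperature will be handled.

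Judge the adjusted arm difference and its one-sided confidence limit against the -10 point margin at both looks, once the level and boundaries have been reconciled. Report the unadjusted difference as supportive.

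The cost is plan wording and one or two degrees of freedom. Stratum and temperature are already collected, so no extra patients, procedures or data are needed. Only the optional epidural term would require a check on timing.
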